213 For subjects not on continuous analgesics, subject has taken the following within 12 hours prior to screening: acetaminophen, NSAIDs, hydrocodone, codeine, tramadol, propoxyphene and/or oxycodone (unless in the form of oxycontin). For subjects not on continuous analgesics, subject has taken oxycontin within 24 hours prior to screening.

*Laboratory Abnormalities*

215 Subject has any other laboratory abnormality, which, in the opinion of the investigator poses a safety risk, will prevent the subject from completing the study, or will interfere with the interpretation of the study results.

230 Subject has laboratory abnormalities during screening, including the following:

- Aspartate aminotransferase (AST) and/or alanine aminotransferase (ALT) > 2 x the upper limit of normal (ULN). If the AST and/or ALT value is between 1.5 and 2 x the ULN without a documented etiology of aminotransferase elevation or without a history of stable elevated aminotransferase for at least 3 months prior to screening.
- Platelet count < 125,000/mm^3
- White blood cell count < 3,000 cells/mm^3
- Absolute neutrophil count < 1500/mm^3
- Estimated creatinine clearance < 30 mL/min (Cockcroft-Gault formula, calculated value to be provided to sites. If the estimated creatinine clearance is between 30 and 50 mL/min (Cockcroft-Gault formula, calculated value to be provided to sites) without a documented etiology for reduced creatinine clearance or without a 3-month history of stable creatinine clearance prior to screening.

*Other*

217 Other investigational procedures while participating in this study are excluded.

218 Female subject is not willing to use highly-effective methods of birth control during treatment and for 6 months after the end of treatment (except if at least 2 years postmenopausal or surgically sterile [hysterectomy, bilateral oophorectomy, or bilateral salpingectomy] or has had a bilateral tubal ligation).

219 Male subject with a partner of child-bearing potential is not willing to use a condom during treatment and for 6 months after the end of treatment (except for men who are surgically sterile).

220 Male subject with a pregnant partner, who is not willing to use a condom to prevent exposure of the fetus to semen during treatment and for 6 months after the end of treatment.

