##### **4.2.2 Exclusion Criteria – Part 2**

- 227 Any clinically significant change in the Part 1 eligibility criteria during the run-in period
- 228 SDAI  $>$  3.3 and  $\leq$  11 on two consecutive visits at least two weeks apart OR SDAI  $>$  3.3 and  $\leq$  11 on two or more separate visits OR SDAI  $>$  11 at any time during the run-in period
- 229 Subject has a clinically significant laboratory abnormality during run-in period which in the opinion of the investigator poses a safety risk, will prevent the subject from completing the study, or will interfere with the interpretation of the study results during the run-in period.

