### **6.4.1 Hepatotoxicity Stopping and Rechallenge Rules**

Subjects with abnormal hepatic laboratory values (ie, alkaline phosphatase [ALP], AST, ALT, and total bilirubin [TBL]) and/or signs/symptoms of hepatitis (as described below) may meet the criteria for withholding of Amgen investigational product or other protocol-required therapies as specified in the Guidance for Industry Drug-Induced Liver Injury: Premarketing Clinical Evaluation, July 2009. Criteria for permanent or conditional withholding of investigational product in the event that a subject develops signs or symptoms of hepatitis during a clinical trial is provided in [Appendix A](#). Criteria for rechallenge of Amgen investigational product and other protocol required therapies after potential hepatotoxicity is provided in [Appendix A](#).

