### **6.4.3 Criteria for Reporting Hepatotoxicity as a Serious Adverse Event**

Subjects who have TBL > 2 x ULN and AST or ALT > 3 x ULN must have the event submitted to Amgen as a serious adverse event within 24 hours following the investigator's knowledge of the event (ie, before additional etiologic investigations have been concluded).

Additional clinical assessments and observations in subjects who experience AST or ALT elevations > 3 x ULN will be performed until abnormalities return to normal or to the subject's baseline levels. Assessments to be performed during this period are outlined in [Appendix A](#).

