### **Criteria for Permanent Withholding of Investigational Product due to Potential Hepatotoxicity**

Investigational product should be discontinued permanently and the subject should be followed for possible drug-induced liver injury, if ALL of the criteria below are met:

- TBL > 2 x ULN or international normalized ratio > 1.5
- AND increased AST or ALT from the relevant baseline value as specified below:

Baseline AST or ALT value	AST or ALT elevation
≤ 1.5 ULN	> 3 x ULN

- AND no other cause for the combination of laboratory abnormalities is immediately apparent; important potential causes for abnormal AST/ALT or total bilirubin values include, but are not limited to the following:
  - obstructive gall bladder or bile duct disease
  - viral or alcoholic hepatitis (eg, hepatitis A/B/C/D/E, Epstein-Barr virus, cytomegalovirus, herpes simplex virus, varicella)
  - progression of malignancy involving the liver (note that metastatic disease to the liver, by itself, should not be used as an explanation for significant AST/ALT elevations)
  - hypoxic or ischemic hepatopathy or congestive hepatopathy in association with significant right-sided heart failure
  - concomitant administration of other hepatotoxins, including drugs that inhibit bilirubin glucuronidation (eg, indinavir, atazanavir, irinotecan) or herbal or dietary supplements
  - heritable disorders causing impaired glucuronidation (eg, Gilbert's syndrome); alpha-one antitrypsin deficiency
  - autoimmune hepatitis
  - nonalcoholic steatohepatitis or other "fatty liver disease"

It should be noted that some of the circumstances above may nevertheless warrant discontinuation of investigational product without requiring assessment for drug-induced liver injury.

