### **Criteria for Conditional Withholding of Investigational Product due to Potential Hepatotoxicity**

For subjects that do not meet the criteria for permanent withholding of investigational product outlined above, investigational product should be withheld if ANY of the following criteria are met, and the subject should be evaluated for drug-induced liver injury:

- Elevation of either AST or ALT according to the following schedule:

Baseline AST or ALT value	AST or ALT elevation
Any	> 8 x ULN at any time
Any	> 5 x ULN but < 8 x ULN for $\geq 2$ weeks
Any	> 5 x ULN but < 8 x ULN and unable to adhere to enhanced monitoring schedule

- OR: clinical signs or symptoms that are, in the opinion of the investigator, consistent with hepatitis (such as right upper quadrant pain/tenderness, fever, nausea, vomiting, jaundice, rash or eosinophilia > 5%). If such signs or symptoms are coupled with ALT or AST elevations > 3 x ULN, investigational product should be withheld.
- OR: total bilirubin > 3 x ULN at any time
- OR: alkaline phosphatase > 8 x ULN at any time

Investigational product should be withheld pending investigation into alternative causes of drug-induced liver injury. If investigational product is withheld, the subject should be followed according to recommendations above for possible drug-induced liver injury. Rechallenge may be considered if an alternative cause is discovered and the laboratory abnormalities resolve to normal or baseline.

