### **Additional Clinical Assessments and Observation**

All subjects in whom investigational product(s) or protocol-required therapies is/are withheld (either permanently or conditionally) due to potential DILI as specified above or who experience AST or ALT elevations >3 x ULN are to undergo a period of “close observation” until abnormalities return to normal or to the subject’s baseline levels.

Assessments that are to be performed during this period include:

- Repeat AST, ALT, ALP, bilirubin (total and direct), and INR within 24 hours
- In cases of TBL > 2x ULN or INR > 1.5, retesting of liver tests, BIL (total and direct), and INR is to be performed every 24 hours until laboratory abnormalities improve

Testing frequency of the above laboratory tests may decrease if the abnormalities stabilize or the investigational product(s) or protocol-required therapies has/have been discontinued AND the subject is asymptomatic.

- Initiate investigation of alternative causes for elevated AST or ALT and/or elevated TBL:
  - Obtain complete blood count (CBC) with differential to assess for eosinophilia
  - Obtain serum total immunoglobulin IgG, Anti-nuclear antibody (ANA), Anti Smooth Muscle Antibody, and Liver Kidney Microsomal antibody 1 (LKM1) to assess for autoimmune hepatitis
  - Obtain serum acetaminophen (paracetamol) levels
  - Obtain a more detailed history of:
    - Prior and/or concurrent diseases or illness
    - Exposure to environmental and/or industrial chemical agents

- 
- Symptoms (if applicable) including right upper quadrant pain, hypersensitivity-type reactions, fatigue, nausea, vomiting and fever
  - Prior and/or concurrent use of alcohol, recreational drugs and special diets
  - Concomitant use of medications (including non-prescription medicines and herbal and dietary supplements), plants, and mushrooms
  - Obtain viral serologies
  - Obtain CPK, haptoglobin, LDH, and peripheral blood smear
  - Perform appropriate liver imaging if clinically indicated
  - Obtain appropriate blood sampling for pharmacokinetic analysis if this has not already been collected
  - Obtain hepatology consult (liver biopsy may be considered in consultation with an hepatologist)

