6.1 Study Time Points

Enrollment Date

A subject's Enrollment Date is defined as the date he or she has met all Part 1 eligibility criteria and the enrollment call in the IXRS system has been completed.

Part 1/Run-in Period

The 24-week period after enrollment and prior to randomization. Specifically, the period begins when a subject initiates treatment with open-label run-in etanercept and/or open-label run-in methotrexate per the eCRF at the same dose he or she was receiving at screening. There are three visits associated with the Run-in Period: Run-in Visit 1, Run-in Visit 2, and Run-in Visit 3.

Run-In Day 1

A subject's Run-In Day 1 is defined as the date of the first dose of IP administration during Part 1.

Run-In Day

A subject's Run-In Day = (Visit Date – Run-In Day 1 date) + 1.

Run-In Failure Date

A subject's Run-In Failure Date is the date the subject ended run-in due to protocol specified criteria per the eCRF.

Randomization Failure Date

A subject's Randomization Failure Date is the date the subject ended run-in due to any reason and was not randomized.

End-of Run-In Date

A subject's End-of Run-In Date is the date subject ends the run-in period per the CRF.

Randomization Date

A subject's Randomization Date is the date when a randomization number is assigned to him or her through the Interactive Voice/Web Response System (IXRS).

Study Day 1

A subject's Study Day 1 is defined as the date of the first dose of IP administration after randomization, or the randomization date if the subject is not dosed.

Baseline

The last measurement for the endpoint of interest taken on or prior to Study Day 1 and after Run-In Visit 3. Hematology and chemistry profiles were not assessed on Day 1; their Run-in Visit 3 values will be used when reporting baseline.

Baseline for Concomitant Medications

Run-In Period Baseline for Concomitant Medications is enrollment date, and Post-Run-In Period Baseline for Concomitant Medications is randomization date.

Study Day

For a given study visit, the study day for a subject is defined as:

Study Day = (Visit Date – Study Day 1 date) + 1.

Part 2/Treatment Period

The up-to 48-week double-blind period beginning with Study Day 1 and ending with the End of Study date.

SDAI Assessment Datea

The SDAI Assessment Date is the latest date of the assessments for Tender Joint Count, Swollen Joint Count, Physician Global Assessment, Patient Global Assessment, and CRP for a given SDAI score.

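### Eligibility admits stable AST/ALT above 1.5 and up to 2 x ULN, but the permanent liver stopping rule has a threshold only for baselines up to 1.5 x ULN

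*Protocol*

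**What the plan says.** **Eligibility.** Section 4.1.2, criterion 230, excludes AST or ALT above 2 x ULN. Between 1.5 and 2 x ULN the exclusion is qualified: "If the AST and/or ALT value is between 1.5 and 2 x the ULN without a documented etiology of aminotransferase elevation", or without a stable history of at least 3 months. A subject with both a documented cause and a stable history is therefore eligible, however the linking word is read. For the run-in, Section 4.2.2, criterion 227, excludes "Any clinically significant change in the Part 1 eligibility criteria during the run-in period".

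**Permanent stop.** Section 6.4.1 sends the reader to Appendix A: "Criteria for permanent or conditional withholding of investigational product in the event that a subject develops signs or symptoms of hepatitis" are provided there. Appendix A requires all of the following:
- bilirubin above 2 x ULN or INR above 1.5;
- "AND increased AST or ALT from the relevant baseline value as specified below";
- no other immediately apparent cause.

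The table for the second item has one row: baseline up to 1.5 x ULN, elevation above 3 x ULN.

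**Conditional withholding.** This rule begins "For subjects that do not meet the criteria for permanent withholding of investigational product outlined above, investigational product should be withheld if ANY" of a list applies. The enzyme triggers cover any baseline: above 8 x ULN, or above 5 and below 8 x ULN either for at least 2 weeks or when enhanced monitoring cannot be followed. The other triggers are signs or symptoms consistent with hepatitis, bilirubin above 3 x ULN and alkaline phosphatase above 8 x ULN. INR is not listed.

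**Reporting and observation.** Section 6.4.3 applies at any baseline: "Subjects who have TBL > 2 x ULN and AST or ALT > 3 x ULN must have the event submitted" as a serious adverse event. Appendix A also requires close observation once AST or ALT exceeds 3 x ULN, including "Repeat AST, ALT, ALP, bilirubin (total and direct), and INR within 24 hours".

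**The concern.** The eligibility rule and the stopping rule do not cover the same subjects. Because the permanent rule needs every criterion, an enzyme whose baseline is in no row of the table cannot satisfy it. The subjects left out already had raised aminotransferases at entry. Everyone takes methotrexate through the 24-week run-in. Two of the three arms, a planned 100 + 50 = 150 of 250 randomized subjects, continue it for up to 48 weeks, and rescue restores it in the third.

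Two further consequences follow. Appendix A bars rechallenge for subjects who clearly meet the permanent criteria, so that bar does not attach to subjects who cannot meet them. Appendix A also does not say which sample is the relevant baseline. The SAP (Section 6.1) states "Hematology and chemistry profiles were not assessed on Day 1; their Run-in Visit 3 values will be used when reporting baseline", but that convention is for reporting, not for stopping decisions at a site.

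**Working it through.** The plan has no figure to reproduce here. The check applies the written rules to example subjects. AST, ALT and bilirubin (TBL) are in multiples of ULN.

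**Who is admitted.** With cause documented and elevation stable, baselines of 1.6, 1.8 and 2.0 are eligible and 2.1 is not.

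**Rules applied**
- Permanent: (TBL > 2 or INR > 1.5) and (AST with baseline ≤ 1.5 is now > 3, or ALT with baseline ≤ 1.5 is now > 3) and no other cause apparent.
- Conditional: AST or ALT > 8; or > 5 and < 8 for at least 2 weeks or without adherence to monitoring; or hepatitis signs or symptoms; or TBL > 3; or alkaline phosphatase > 8.
- Section 6.4.3 report: TBL > 2 and (AST or ALT) > 3.

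**Worked cases.** All assume no symptoms, no other apparent cause, alkaline phosphatase not above 8 and monitoring followed. INR is taken as not above 1.5 unless shown.

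| On-study pattern | Baseline AST/ALT 1.2/1.4 | 1.2/1.8 | 1.7/1.8 |
|---|---|---|---|
| 1. ALT 4.5, AST 4.0, TBL 2.5 | permanent stop | permanent stop, through AST | neither rule |
| 2. ALT 4.5, AST 2.5, TBL 2.5 | permanent stop | neither rule | neither rule |
| 3. ALT 4.5, AST 4.0, TBL 1.0, INR 1.6 | permanent stop | permanent stop, through AST | neither rule |
| 4. ALT 7.0, AST 6.0, TBL 2.5, week 1 | permanent stop | permanent stop, through AST | neither rule until 2 weeks, then conditional only |

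In case 1 at baseline 1.7/1.8, TBL 2.5 > 2 meets the first criterion, but both baselines exceed 1.5, so no row applies and the permanent rule fails. The conditional rule fails because 4.5 is not above 5 and 2.5 is not above 3. In case 3 the Section 6.4.3 trigger also fails, because TBL 1.0 is not above 2.

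With both enzymes in the band the permanent rule fails at every on-study level. At 9 x ULN only conditional withholding applies.

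**Uncovered zone.** For an enzyme in the band: values above 3 and up to 5 x ULN with no time limit, and above 5 and below 8 x ULN for under 2 weeks, when TBL is above 2 and up to 3 x ULN or INR exceeds 1.5.

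**With the row extended to 2 x ULN.** ALT exceeds 3 in all four patterns and every baseline shown is at or below 2, so all twelve cells become a permanent stop. The cases illustrate the logic; they are not frequencies.

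**Rise implied by the 3 x ULN trigger:** 3/1.5 = 2.0-fold; 3/1.8 = 1.67-fold; 3/2.0 = 1.5-fold.

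**The case against.** - **Appendix A is a synopsis.** It describes itself as a reference summary of a regulatory guidance, and Section 6.4.1 also cites that guidance, so a threshold for higher baselines might exist there. But Section 6.4.1 says the withholding criteria are provided in Appendix A, and sites will act on that text.
- **A table row may have been lost in text conversion.** This cannot be fully excluded. The neighbouring conditional table kept all three rows, and nothing in the text points to a missing one. The sponsor can check at once.
- **A documented cause may count as another cause.** This partly stands. For some admitted subjects the third criterion would block a permanent stop even with the row extended. But a known reason for a stable 1.8 x ULN need not explain a new rise combined with raised bilirubin or INR, and where it does, the third criterion already deals with it.
- **Other safeguards exist.** They do. Tests are repeated within 24 hours, then every 24 hours while bilirubin exceeds 2 x ULN or INR exceeds 1.5. A hepatology consult is required. The investigator or sponsor can stop product at any time. Drug-induced liver injury can be reported as a medically important serious event even when the Section 6.4.3 trigger is not met. The list of hepatitis signs is broad, and the examples assume none is present. These limit the harm, but they are observation, reporting or judgment rather than a threshold that requires stopping.
- **The band's threshold is the sponsor's choice.** This stands. The documents fix none, and a 1.5-fold rise from 2.0 x ULN is modest.

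**Conclusion.** The concern holds. As written, an enzyme with baseline above 1.5 and up to 2 x ULN cannot trigger the permanent stop, and a subject with both enzymes there can never meet that rule. With only one enzyme in the band, the other can still trigger it. The conditional rule fills part of the gap but leaves the zone described above. Criterion 227 partly limits drift above 2 x ULN during the run-in, but a stable, permitted elevation is not a change and passes through.

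The gap is narrow and does not bear on the primary analysis. It should still be fixed, because it weakens a safety stopping rule for subjects who enter with raised enzymes. The conclusion assumes the single-row table is complete as published. The documents give no number of affected subjects, and none is estimated here. The unnamed baseline sample is missing detail that belongs in the same correction.

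**What to change.** In Appendix A, change the baseline entry in the permanent-withholding table so that it covers every baseline eligibility allows: either any baseline or up to 2 x ULN. Keep the trigger above 3 x ULN, which Section 6.4.3 already uses whatever the baseline, unless the sponsor's safety group sets a different value for the band above 1.5 and up to 2 x ULN. Add one sentence naming the sample, screening or Run-in Visit 3, that serves as the relevant baseline.

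The cost is one table cell and one sentence in a protocol amendment, with no added tests or subjects. A few subjects with raised baselines may be stopped sooner, after a rise as small as just over 1.5-fold. The bilirubin/INR criterion and the no-other-cause criterion still apply and limit this. Section 8.1 describes continued assessments after product is stopped at the subject's request; the same follow-up can be offered here, so a subject taken off product need not be lost to the Week 48 assessment.

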### **Criteria for Conditional Withholding of Investigational Product due to Potential Hepatotoxicity**

For subjects that do not meet the criteria for permanent withholding of investigational product outlined above, investigational product should be withheld if ANY of the following criteria are met, and the subject should be evaluated for drug-induced liver injury:

- Elevation of either AST or ALT according to the following schedule:

Baseline AST or ALT value	AST or ALT elevation
Any	> 8 x ULN at any time
Any	> 5 x ULN but < 8 x ULN for $\geq 2$ weeks
Any	> 5 x ULN but < 8 x ULN and unable to adhere to enhanced monitoring schedule

- OR: clinical signs or symptoms that are, in the opinion of the investigator, consistent with hepatitis (such as right upper quadrant pain/tenderness, fever, nausea, vomiting, jaundice, rash or eosinophilia > 5%). If such signs or symptoms are coupled with ALT or AST elevations > 3 x ULN, investigational product should be withheld.
- OR: total bilirubin > 3 x ULN at any time
- OR: alkaline phosphatase > 8 x ULN at any time

Investigational product should be withheld pending investigation into alternative causes of drug-induced liver injury. If investigational product is withheld, the subject should be followed according to recommendations above for possible drug-induced liver injury. Rechallenge may be considered if an alternative cause is discovered and the laboratory abnormalities resolve to normal or baseline.

### **Criteria for Rechallenge of investigational product after Potential Hepatotoxicity**

The decision to rechallenge the subject should be discussed and agreed upon unanimously by the subject, principal investigator, and Amgen.

If signs or symptoms recur with rechallenge, then investigational product should be permanently discontinued. Subjects who clearly meet the criteria for permanent discontinuation should never be rechallenged.

---

## **Drug-induced Liver Injury Reporting & Additional Assessments**

### **Reporting**

To facilitate appropriate monitoring for signals of DILI, cases of concurrent AST or ALT and TBL according to the criteria specified in [Section 6.4](#) (3 x ULN for AST/ALT and 2 x ULN for TBL) require the following:

- The event is to be reported to Amgen as a serious adverse event within 24 hours of discovery or notification of the event (ie, before additional etiologic investigations have been concluded)
- The appropriate CRF (eg, Adverse Event CRF) that captures information necessary to facilitate the evaluation of treatment-emergent liver abnormalities is to be completed and sent to the Amgen.

Other events of hepatotoxicity and potential DILI are to be reported as serious adverse events if they meet the criteria for a serious adverse event defined in [Section 9.2.2](#).

